2.3 Potential Risks and Benefits

2.3.1 Potential Risks

The risks and discomforts of this study include risks associated with the vaccine, administration of the vaccine, the risks associated with study procedures (blood drawing and nasal and throat swabs) and possible loss of confidentiality.

In placebo-controlled trials in children, inactivated seasonal vaccines are associated with mild local pain at the site of administration and occasional systemic symptoms. According to the package insert, systemic symptoms like fever occur in 14.3% of infants and 7% of children. Likewise, some irritability (54.1%) was seen in infants, with abnormal crying occasionally reported. The most common adverse events reported remain local symptoms, with injection site pain (57-66%), tenderness (54.1%), erythema (37.3-34.1%), and swelling (21.6-24.8%) common. As influenza vaccination is considered the standard of care, these risks will be no greater than what children will be exposed to through current best practice recommendations [1].

During the swine influenza vaccine campaign of 1976, about 10 per 1,000,000 vaccine recipients in excess of the background rate developed the paralytic illness called Guillain-Barre Syndrome (GBS). In the subsequent decade, no association between seasonal influenza vaccine and GBS was found. More extensive investigations of this potential association occurring in the 1990s revealed that there was a small but detectable risk of GBS in the 6 weeks following seasonal

influenza immunization: an attributable risk of approximately 1 per 1,000,000, adjusted for potential confounders. In the period since the Vaccine Adverse Event Reporting System (VAERS) was established in 1990, the rates of GBS reports following influenza vaccination have declined substantially. The annual reporting rate in that period was highest in the 1993-1994 influenza season (1.7 per 1,000,000 vaccinees) and lowest in the last season analyzed in the report, 2002-2003 (0.4 per 1,000,000 vaccinees) [30]. GBS is thus considered highly unlikely after influenza vaccination and, as vaccination is considered the standard of care for all infants ≥ 6 months of age and children, is not a greater risk than children would be exposed to receiving standard pediatric care [1].

All blood will be drawn by experienced and trained pediatric nurses or physicians, with pain minimized through comforting and distraction techniques. Only the minimum amount of blood necessary to achieve the study objectives will be obtained, with the blood volume being within a level accepted as safe (Table 1). As a child's total blood volume is related to body weight, we have chosen a weight based approach to determine the volume of blood to be obtained. This will allow us to optimize our likelihood of being able to accomplish the study objectives while still prioritizing the safety of the child (see Scientific Rationale section). The proposed blood draws in this protocol impose a maximum upper limit of 1 mL/kg on any single draw (about 1.25% of estimated TBV), with a maximum of 3 mL/kg (about 3.75% of estimated TBV) over any 8 week period for all pediatric patients (Table 1). This volume remains well below the upper limit of 10% of total blood volume in an 8 week period and is consistent with the available evidence on what will present minimal risk to children [31] while still providing enough PBMCs to perform the in depth analysis of CD4 T and B cell specificity and functional capacity as well as antibody responses required for this study.

Drawing blood causes transient discomfort and may cause fainting. Bruising at the blood draw site may occur but can be prevented or mitigated by applying direct pressure to the draw site for several minutes. The use of alcohol swabbing and sterile equipment will make infection less likely at the site where blood will be drawn. The volume of blood per kg body weight being drawn is within a range considered safe. However, some older children may develop transient lightheadedness following blood drawing as a result of a vaso-vagal reflex. This will be discussed with parents/LARs at the time of the consent. If such a reaction occurs, the child will be laid down, have a blood pressure obtained, and be observed until the symptoms pass (but for at least 10 minutes).

Nasal swabs and washes can be uncomfortable and may cause gagging or occasionally minor brief irritation and rarely transient bleeding. Long term side effects from these procedures are considered extremely unlikely.

Personal health information of the subjects will be collected to determine eligibility and to evaluate outcomes throughout the study. Research personnel will make every effort to keep this information confidential. Still, a risk of participation is that the confidentiality of this information could be lost.

2.3.2 Known Potential Benefits

Although administration of influenza vaccines may result in the development of immunity that will prevent influenza infection, this intervention is considered the standard of care and presumably would occur regardless of study participation. Infants presenting with influenza-like illness during influenza season will receive influenza testing as part of their evaluation, which has the potential to diagnose and allow for the treatment of an active influenza infection. There are no other direct potential benefits to study participation.

3 OBJECTIVES AND OUTCOME MEASURES

3.1 Study Objectives

Primary Objective

To evaluate the relationship between influenza virus exposure, infection and vaccine history, and CD4 T cell reactivity in a cohort of children with well documented influenza exposures.

Exploratory Objectives

Determine the durability and breadth of the CD4 T cell and B cell/antibody responses and evaluate for relationships between response durability and factors such as age and exposure history.

3.2 Outcome Measures

3.2.1 Primary Outcome Measures

- Assess the frequency and functional potential of CD4 T cell responses on a single cell level using full spectrum flow cytometry following either infection or inactivated influenza vaccine administration, with stratification by age and exposure history

[figure not shown]
3.2.2 Exploratory Outcome Measures

- Evaluate the humoral immune response that develops in response to infection or IIV vaccination using ELISA, microneutralization, and HAI assays with stratification by age and exposure history
- Determine the frequency of influenza-specific plasmablasts and memory B cells by ELISPOT and flow cytometry, with expression of monoclonal antibodies from cloned variable genes of single cells
- Determine the influence of the CD4 T cell response on the breadth and avidity of the post-vaccination antibody response
- Compare the cellular phenotype and functional potential observed at the day 24 post vaccination visit in study year one with that present at the prevaccination study visit in year 2 and 3

[figure not shown]

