To evaluate the relationship between influenza virus exposure through infection and vaccination and CD4 T cell reactivity in a cohort of children with well documented influenza exposures

Primary Outcome Measures:

- Assess the frequency and functional potential of CD4 T cell responses on a single cell level using full spectrum flow cytometry following either infection or inactivated influenza vaccine administration, with stratification by age and exposure history

Exploratory Objectives

[figure not shown]
Determine the durability and breadth of the CD4 T cell and B cell/antibody responses and evaluate for relationships between response durability and factors such as age and exposure history.

Exploratory Outcome Measures:

[figure not shown]
- Evaluate the humoral immune response that develops in response to infection or IIV vaccination using ELISA, microneutralization, and HAI assays with stratification by age and exposure history
- Determine the frequency of influenza-specific plasmablasts and memory B cells by ELISPOT and flow cytometry, with expression of monoclonal antibodies from cloned variable genes of single cells
- Determine the influence of the CD4 T cell response on the breadth and avidity of the post-vaccination antibody response
- Compare the cellular phenotype and functional potential observed at the day 24 post vaccination visit in study year one with that present at the prevaccination study visit in year 2 and year 3

Study Schematic

- **Cohort 1A and 1B: Children between 3 and 12 months of age (6 months of age or greater required for participation in the vaccination cohort 1A)**

- **Cohort 2A and 2B: Greater than 12 months of age, birth date after 2009 (early exposure to pH1N1)**
 - Cohort 2A will enroll 35 children <3 years of age and 25 children >=3 years of age
- **Cohort 3A and 3B: Birth date between 2006 and 2009**
- **Cohort 4A and 4B: Birth date between 2003 and 2006 (early exposure to previous seasonal H1N1 strains)**

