the children in cohorts 2 through 4 of the vaccination arm of the study will have previously received at least 2 doses of influenza vaccine, and thus will only require a single vaccine dose. However, children presenting with acute influenza infection may not yet have received 2 vaccine doses and thus may require both a priming and a booster dose of vaccine in year 2 of the study [29]. The second age cohort (> 12 months, birthdate after 2009) will likely have had exposure to the 2009 pandemic virus in early childhood. The third age cohort (birthdate between 2006 and 2009) may or may not have had early exposure to the 2009 pandemic virus, while the final cohort (birthdate between 2003 and 2006) will likely have had early childhood exposures to the previously seasonal H1N1 viral strains.

Blood draws will be obtained on study enrollment, day 8 (+2d), and day 24 (+/- 4d) post enrollment as depicted in Figure 1. The blood draw on study enrollment will evaluate influenza-specific immunity at the time of study entry. The blood draw on day 8 (+2d) post-vaccination will allow examination of each subject as CD4 T cell and plasmablast responses are peaking, while the day 24 (+/- 4d) time point will capture the peak of the neutralizing antibody response and allow us to examine CD4 T cell responses as they contract. All subjects will be followed through to the subsequent influenza season, at which point they will be rechallenged with IIV. Blood draws will again be obtained pre-vaccination and at days 8 (+2d) and 24 (+/- 4d) post vaccine administration, with the pre-vaccination blood draw providing a method to assess for undocumented influenza infection over the prior year. Upon completion of the planned follow up visits, subjects will be offered the opportunity to participate in the study for an additional influenza season to enable collection of longitudinal data on the development of early life anti-influenza immunity.

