Visit 4 (Season 2 day 0): Subjects will be asked to return to the VRU the following fall to receive seasonal influenza vaccination. At this time, the ICF, study requirements and any AE or other illnesses will be reviewed. Subjects will have an interval medical history obtained, including vaccinations and a review of all medications. Any illness memory aids returned will be reviewed to determine if the parent/LAR recorded any symptoms consistent with influenza-like illness that were not reported to study personnel. Subject weight and vital signs will then be obtained and a targeted physical exam performed as indicated by medical history. Following this a sample of peripheral venous blood will be obtained if able. Subjects will then be vaccinated with seasonal IIV. Parents/LARs will use the memory aids to document the symptoms of any illnesses that occur and will be instructed to call the study coordinator if symptoms consistent with an influenza-like illness are present.

Visit 4.5: Vaccine booster visit (Season 2 day 28 +14 days):

Children <9 years of age acutely infected with influenza (cohort B) who have not appropriately received 2 or more total doses of influenza vaccine will present to the VRU to receive their influenza vaccine booster dose on day 28 (+14) following the initial influenza vaccination (Visit 4). At this time, ICF, study requirements, any returned illness memory aids, and any adverse events or other illnesses will be reviewed. An interim medical history, including vaccinations, will be obtained and medications reviewed. A targeted PE will be completed and vital signs and weight obtained. Then a dose of seasonal IIV will be administered intramuscularly.

Visit 5 (Season 2 day 8/36 + 2 days): Subjects may return to the VRU or have a home visit completed on day 8 (+2) following IIV administration (this will be about day 36 following the initial vaccination for children requiring 2 doses of influenza vaccine). At this time, the ICF, study requirements, any returned illness memory aids that document recent symptoms of illness and any adverse events or other illnesses will be reviewed. An interim medical history, including vaccines, will be obtained and medications reviewed. Vital signs and subject's weight will be obtained and a targeted PE performed. Following this a sample of peripheral venous blood will be obtained if able.

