Visit 6 (Season 2 day 24/52 +/- 4 days): Subjects may return to the VRU or have a home visit completed on day 24 (+/-4) following revaccination with IIV (this will be about day 52 following the initial vaccination for children requiring 2 doses of influenza vaccine). At this time, the ICF, study requirements, any returned illness memory aids that document recent symptoms of illness and any adverse events or other illnesses will be reviewed. An interim medical history, including vaccines, will be obtained and medications reviewed. Vital signs and subject's weight will be obtained and a targeted PE performed. A sample of peripheral venous blood will be obtained if able.

Optional 1 year Follow-up Visit 1 (Season 3 day 0) -: Subjects will be asked to return to the VRU the following fall to receive seasonal influenza vaccination. At this time, the ICF, study requirements and any AE or other illnesses will be reviewed. Subjects will have an interval medical history obtained, including vaccinations, and a review of all medications. Any illness memory aids returned will be reviewed to determine if the parent/LAR recorded any symptoms consistent with influenza-like illness that were not reported to study personnel. Subject vital signs and a weight will be obtained and a targeted physical exam performed as indicated by medical history. Following this a sample of peripheral venous blood will be obtained if able. Subjects will then be vaccinated with seasonal IIV. Parents/LARs will use the memory aids to document the symptoms of any illnesses that occur and will be instructed to call the study coordinator if symptoms consistent with an influenza-like illness are present.

Optional 1 year Follow-up Visit 2 (Season 3 day 8+2 days) - Subjects may return to the VRU or have a home visit completed on day 8 (+2) following IIV administration. At this time, the ICF, study requirements, any returned illness memory aids that document recent symptoms of illness and any adverse events or other illnesses will be reviewed. An interim medical history, including vaccines, will be obtained and medications reviewed. Vital signs and subject's weight will be obtained and a targeted PE performed. Following this a sample of peripheral venous blood will be obtained if able.

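### The year 3 leg of the cross-season comparison spans the season 2 vaccination, so it cannot separate persistence from boosting; Visit 6 is the reference that can

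*Combined protocol and SAP*

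**What the plan says.** The exploratory objective in section 3.1 is to "Determine the durability and breadth of the CD4 T cell and B cell/antibody responses" and to relate durability to factors such as age and past exposure. The last exploratory outcome in section 3.2.2 takes its reference from the first season: "Compare the cellular phenotype and functional potential observed at the day 24 post vaccination visit in study year one". It sets this one reference against two later samples, in the words "with that present at the prevaccination study visit in year 2 and 3". The Protocol Summary gives the same comparison: "with that present at the prevaccination study visit in year 2 and year 3".

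The visit sequence is set out in sections 2.2 and 7.3:

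- Section 2.2: "All subjects will be followed through to the subsequent influenza season, at which point they will be rechallenged with IIV".
- Visit 4 (season 2, day 0): "Following this a sample of peripheral venous blood will be obtained if able. Subjects will then be vaccinated with seasonal IIV". The optional-season Visit 1, in the fall of season 3, follows the same order.
- Visit 4.5: a second season 2 dose, only for cohort B children under 9 years who have not had two doses in total.
- Visit 6: children may come to the unit or "have a home visit completed on day 24 (+/-4) following revaccination with IIV". Blood is drawn if possible. For two-dose children this visit falls at about day 52, that is, 24 days after the second dose.

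Section 11.4 plans group comparisons at each time point, linear models of change from baseline, and a mixed model over all time points. It names no contrast from day 24 of one season to the pre-vaccination visit of the next, and no term for doses given in between.

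**The concern.** A persistence contrast needs an interval in which the antigen is not given again. The first interval in this outcome meets that condition as far as scheduled doses go. The second does not, because the season 2 IIV lies inside it for every child. A year 3 level close to the year 1 day 24 level could mean that the response lasted, or that it waned and was restored by the season 2 dose. The contrast alone cannot tell these apart.

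The number of intervening doses also differs between children. It is one for all of cohort A and for most or some of cohort B (the split is not given), and two for cohort B children under 9 without two earlier doses. Dose number therefore varies with arm, age and vaccine history, which are the factors the objective wants to relate to durability. A subgroup difference in the year 3 leg could come from the boost even if waning were the same in both groups.

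**Working it through.** **Scheduled doses inside each interval** (sections 2.2 and 7.3)

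| Interval | Doses, cohort A | Doses, cohort B |
|---|---|---|
| Year 1 day 24 (Visit 3) to Visit 4 draw | 0 | 0 |
| Year 1 day 24 (Visit 3) to optional-season Visit 1 draw | 1 | 1, or 2 if Visit 4.5 applies |
| Season 2 day 24 (Visit 6) to optional-season Visit 1 draw | 0 | 0 |

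The third row is zero for two-dose children as well, because their Visit 6 is timed from the second dose (28 + 24 = 52). The season 3 dose follows the optional-season Visit 1 draw and does not enter.

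**Size.** The documents give no persistence fraction, no fold rise and no SD, so there is no stated figure to reproduce. Assume:

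- r = fraction of the day 24 level left at the next pre-vaccination draw, the same in both intervals;
- b = fold rise from the season 2 pre-vaccination level to season 2 day 24.

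Then:

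- year 2 pre / year 1 day 24 = r
- year 3 pre / year 1 day 24 = r × b × r
- year 3 pre / season 2 day 24 = r
- two-year persistence without the boost = r × r

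The year 3 leg overstates r × r by (r × b × r) / (r × r) = b.

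| r | r × r | b = 1 | b = 1.5 | b = 2 | b = 4 |
|---|---|---|---|---|---|
| 0.3 | 0.09 | 0.09 | 0.135 | 0.18 | 0.36 |
| 0.5 | 0.25 | 0.25 | 0.375 | 0.50 | 1.00 |
| 0.7 | 0.49 | 0.49 | 0.735 | 0.98 | 1.96 |
| 0.9 | 0.81 | 0.81 | 1.215 | 1.62 | 3.24 |

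At r = 0.7 and b = 2 the contrast reads 0.98, apparently almost no loss, while r × r is 0.49.

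**Subgroup differences.** Take two groups with the same r = 0.5 but b = 1.5 and b = 2. Their year 3 ratios are 0.375 and 0.50, an apparent difference in durability of 0.50 / 0.375 = 1.33-fold with no difference in waning. Measured from Visit 6, both give 0.5.

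**Children available.** Section 5 plans 20 + 60 + 30 + 30 = 140 children in A and up to 4 × 20 = 80 in B, 220 in all, which agrees with the stated total. With two-thirds expected in the optional year, about 220 × 2/3 = 147 children (93 A, 53 B) could supply the second interval, before any failed draws.

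**The case against.** **The outcome never uses the word durability.** It speaks of phenotype and functional potential, and section 2.2 also wants to know whether the CD4 repertoire is remodelled over time and how early-life immunity develops. A cumulative year 3 sample is relevant to those questions. This stands, and it is a reason to keep the year 3 comparison under a descriptive label. It does not supply a year 3 measure of persistence, and no other listed outcome does so across seasons.

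**A reader might infer that the whole outcome measures re-boosting instead of persistence.** The documents do not support that. The year 2 leg is drawn before the season 2 dose and is a valid persistence contrast. The year 3 sample comes a year after the season 2 visit, so it is a mixture and not a pure boost.

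**A reader might infer that Visit 6 is collected but goes unanalysed, or that section 11.4 has only between-group tests.** Neither is so. Section 11.4 analyses responses 24 days after revaccination, and its models of difference or fold change from baseline use a within-child response. What is missing is narrower: Visit 6 is not the reference for year 3, and the day 24 to pre-vaccination change is not named.

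**A reader might infer that cohort B is excluded**, because the reference is called post-vaccination and B children are infected in year 1. Section 7.3 defines Visit 3 as day 24 after infection or final vaccination, and section 11.4 uses the same shorthand for both arms. This is loose wording that needs clarifying, not an exclusion.

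**The outcome is exploratory, the study has no powered hypothesis, and the samples can be re-analysed later.** All true. This limits the importance of the point, but a correction that needs only wording is still better made before the data are seen.

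**Conclusion.** The point holds for the year 3 leg only. That leg contains at least one scheduled IIV dose for every child and two for some, so it cannot separate persistence from the season 2 boost, and neither section 3.2.2 nor section 11.4 re-anchors it.

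Under the simple model the overstatement of two-year persistence is the factor b: 1 to 4 times over the range shown, and none at b = 1. That size rests on assumed r and b, on a constant r, and on a response that can be read as a single level. It carries over less directly to a multi-marker phenotype. Infection between seasons can disturb either interval, and re-anchoring does not remove that.

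The primary outcome is not affected. The second interval depends on an optional year that is subject to funding and drawn from children who choose to stay.

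**What to change.** Reword the outcome in section 3.2.2 and the Protocol Summary, and name the analysis in section 11.4:

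1. First persistence contrast: Visit 3, stated as day 24 after vaccination or infection, to the Visit 4 pre-vaccination draw.
2. Second persistence contrast: Visit 6 to the pre-vaccination draw at the optional-season Visit 1, in children who enrol in that year.
3. Analyse both as within-child changes, using paired log ratios or a mixed model with a child effect. The model written in section 11.4 has a random term indexed by time and none for the child, so that term would have to be added.
4. Keep year 1 day 24 versus year 3 pre-vaccination as a descriptive, cumulative comparison after revaccination, and report the number of season 2 doses alongside it.

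The cost is wording in the outcome list and the analysis section. Every sample is already scheduled, and no visit, blood draw or dose changes.
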